OHSRP	Office of Human Subjects Research Protections
OMIM	Online Mendelian Inheritance in Man
PhD	Doctor of Philosophy
PI	Principal Investigator
RCD	Rod-cone dystrophy
RN	Registered Nurse
RP	Retinitis Pigmentosa
RPE	Retinal Pigment Epithelium
SAE	Serious Adverse Event
ScM	Master of Science
SOP	Standard Operating Procedures
VA	Visual Acuity
VFQ	Visual Field Questionnaire

PRÉCIS

Objective: Rod-cone dystrophy (RCD) is a term applied to a number of genetically heterogeneous diseases presenting with night vision abnormalities, visual field defects and reduced rod electroretinography responses. Enhanced S-Cone syndrome (ESCS) is a rare autosomal recessive retinal disease with a developmental and a degenerative aspect. Macular cystic changes, often florid and usually resulting in a reduction of central acuity, are frequently associated with both diseases. The reason for this association is not well understood. Acetazolamide (Diamox) and Dorzolamide (Trusopt) have been reported to have variable success in reducing these cystic changes but the effect is frequently inadequate. The objective of this study is to evaluate the safety and potential efficacy of Interferon (IFN) gamma-1b administered topically for macular edema/retinal schisis cysts in RCD and ESCS. Possible disease-related pathophysiologic mechanisms will be explored using induced pluripotent stem cell (iPSC) protocols leading to iPSC-derived retinal pigment epithelium (RPE) and photoreceptor generation.

Study Population: Up to five participants with RCD with significant macular cystic changes and up to five participants with ESCS with significant macular cystic changes will be enrolled to receive IFN gamma-1b administered topically in one eye. However, up to an additional two participants may be enrolled in order to obtain the five participants in each disease group to be included in the primary analysis if any participants withdraw from the study prior to receiving five days of treatment.

Design: This is a single-center, prospective, uncontrolled, unmasked pilot Phase I/II study of the safety, tolerability and possible efficacy of IFN gamma-1b in participants with RCD and ESCS and macular cystic changes. One eye of up to five participants with RCD with significant macular cystic changes and up to five participants with ESCS with significant macular cystic changes [evidenced by optical coherence tomography (OCT) >275 microns central macular thickness and/or disruption of foveal contour] will receive topical IFN gamma-1b instilled as drops on the cornea. The initial stage of the study will include two participants from each disease category. Once all four participants have completed the 8-week visit, enrollment will be halted. Safety Adverse Event Review Committee members unaffiliated with the study will review the

data as a preliminary assessment of safety and efficacy and to determine whether enrollment should continue. If the committee determines enrollment will continue, three additional participants with RCD and three participants with ESCS will be enrolled. The study will be completed once the final participant has received one year of follow-up.

Outcome Measures: The primary outcome measure related to the safety and tolerability of IFN gamma-1b administered topically at the prescribed dosage for macular cystic changes in participants with RCD and ESCS will be assessed by the number and severity of adverse events related to the IP and the number of withdrawals at 52 weeks (one year) post-administration. Additional safety of IFN gamma-1b administered topically in participants with RCD and ESCS will be determined from the assessment of retinal function, ocular structure and occurrence of adverse events at all time points. Secondary outcomes include changes in visual function including visual acuity and microperimetry, and retinal imaging with OCT and fluorescein angiography.

1.0 INTRODUCTION/SCIENTIFIC RATIONALE

RCD is a broad category of genetically heterogeneous diseases that includes many different forms of primary photoreceptor abnormalities – typically affecting rods first and cones later. Retinitis pigmentosa (RP) is the most common form of RCD. The prevalence is in the range of 1:3000–1:5000.¹ The natural history of the disease involves progressive visual field loss and difficulties with night vision. Reduction in central vision can develop secondary to macular atrophy in advanced stages of the disease or due to cystic macular changes at any stage. Early studies on macular changes in RP gave macular edema a prevalence of around 13% based on clinical examination and fluorescein angiography.^{2,3} Cystic macular changes were noted in up to one third of patients on OCT with visual loss that is correlated with the degree of macular thickening.^{4,5} The cystic changes are frequently bilateral and may respond to treatment with carbonic anhydrase inhibitors (CAIs).⁶⁻⁸ Some patients do not respond well to CAI therapy and a rebound effect has been noted with extended use.⁹

ESCS (OMIM 268100; <http://www.ncbi.nlm.nih.gov/omim/> Online Mendelian Inheritance in Man; NCBI, Bethesda, MD) is a rare autosomal recessive disease primarily associated with mutations in the gene *NR2E3* (OMIM 604485). The disorder was first recognized as a separate entity by Jacobson and Marmor in 1990^{10,11} and association with the *NR2E3* gene was described by Haidar et al. in 2000.¹² The phenotype is variable but early hemeralopia, visual field constriction, nummular pigmentary clumping in the retinal midperiphery and pathognomonic electroretinographic changes aid in suspecting the diagnosis.^{10,11,13-15} The disease is commonly associated with significant central retinal cystic changes showing variable response to treatment with topical or systemic CAIs.^{13,14,16-19} No leakage has been noted on fluorescein angiography, leading Audo et al. to ascribe these changes to schisis rather than edema.¹³ The exact mechanism behind these often dramatic cystoid changes, with associated reduction in acuity, is still elusive.

Milam et al. reported on the histopathology in a 77-year-old patient with ESCS (confirmed molecularly) indicating that the retina was disorganized with densely packed cones in the center (most of which were labeled with S-cone opsins). They note that the peripheral retina was degenerative with no rods identified. The RPE was variably depigmented.²⁰

Multiple investigators have studied electroretinographic responses in ESCS. The main findings include almost absent rod responses, delayed scotopic maximal response and photopic flash responses (thus the two waveforms look similar in shape) and a more robust S-cone response compared to the reduced L- and M-cone responses.^{10,11,13,14,21-24} Pattern electroretinography showed variable reduction in amplitude and delay of the P50 component.^{13,23} Variable degrees of dyschromatopsia have been reported on color vision testing with many patients demonstrating relative tritan axis sparing and moderately elevated protan and deutan thresholds.¹³

The *NR2E3* gene was identified in 1999 as a photoreceptor cell-specific nuclear receptor.²⁵ The association of mutations in this nuclear receptor gene with ESCS was made by Haider et al.¹² The molecular biology of this gene is also of interest because of the role it plays in photoreceptor development, differentiation, and maintenance.^{20,26-34} It has also been noted that mutations in other genes that interact with *NR2E3* can, less commonly, cause a similar phenotype.³⁵ Recently, Mustafi et al. reported on defective photoreceptor phagocytosis in a mouse model of ESCS as a possible contributor to the progressive degeneration.³⁶ They do not indicate defective RPE but rather an abnormal interaction between the photoreceptors and the RPE. Personal communication with [name] indicates that *NR2E3* is part of the adult RPE transcriptome (based on work by Strunnikova et al.).³⁷ All previous reports had indicated that the gene is photoreceptor specific. Given the above body of work, it would be very helpful if iPSC-derived photoreceptor and RPE cells were available to further study the disease mechanisms.

The fluid transport role of the RPE is important in the control of subretinal fluid.³⁸ The active “pump” role of the RPE is believed to be important in the maintenance of retinal attachment and fluid absorption. This role can be modified with the use of medications.³⁹ *In vivo* rodent studies have shown that IFN gamma-1b applied to the anterior surface of the eye results in significant, rapid decrease in retinal detachment volume.⁴⁰ A number of National Eye Institute (NEI) protocols address the question of the safety (and possible efficacy) of topical IFN gamma-1b for the treatment of macular edema in different disease models (Central Serous Chorioretinopathy (CSC) in NIH protocol 12-EI-0013; Uveitis in NIH protocol 09-EI-0191 and NIH protocol 11-EI-0167). Topical IFN gamma-1b was first evaluated in uveitic macular edema at the NEI (NIH protocol 09-EI-0191). This pilot, phase I, dose-escalation study found topical IFN

gamma-1b to be safe and well tolerated with no systemic adverse events or abnormal laboratory values (unpublished data). Two participants received 10 micrograms (μg) of topical IFN gamma-1b (one instillation), two participants received 20 μg (two instillations) and one participant received 30 μg (three instillations). Variable changes in retinal thickness were noted using OCT testing; for that study, topical IFN gamma-1b was administered as a one-time instillation or series of instillations and OCT testing was performed over a three-hour time period. We propose to study the safety and potential efficacy of topical IFN gamma-1b for macular cystic changes in the setting of RCD and ESCS. In the proposed protocol, ESCS would serve as a model of hereditary retinal diseases associated with significant macular cystic/schisis changes and RCD would serve as a model for the more common presentation of macular changes in a hereditary retinal degeneration.

2.0 STUDY OBJECTIVES

The primary objective of this study is to explore the safety, tolerability, and possible efficacy of the topical application of IFN gamma-1b used as a therapeutic option in patients with macular cystic changes associated with RCD and ESCS. Participants will be assessed for systemic and ocular side effects. The study is a safety trial but will also provide information about the possible therapeutic effect of IFN gamma-1b in a model of florid cystic macular edema and in hereditary retinal degenerations. Insight into the pathophysiology of the diseases will be possible by obtaining skin biopsy and blood samples for stem cell derived studies.

3.0 PARTICIPANTS

Up to five participants with RCD with significant macular cystic changes and up to five participants with ESCS with significant macular cystic changes will be enrolled to receive topical IFN gamma-1b in one eye. However, up to an additional two participants may be enrolled in order to obtain the five participants in each disease group to be included in the primary analysis if any participants withdraw from the study prior to receiving five days of treatment.

The inclusion and exclusion criteria are outlined in the following sections.

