7.0 OUTCOME MEASURES

7.1 Primary Outcome Measures

The primary outcome measure related to the safety and tolerability of IFN gamma-1b administered topically at the prescribed dosage for macular cystic changes in participants with RCD and ESCS will be assessed by the number and severity of adverse events related to the IP and the number of withdrawals.

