8.1 Analysis

All reported adverse events will be tabulated and presented by system organ class, severity and relationship to study therapy.

Secondary outcomes will be presented for each participant and tabulated over time, as described in Section 7.2. Additionally, these outcomes will compare the changes within the study eye from baseline and the changes between the study eye and control eye over time.

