8.2 Sample Size

No formal sample size calculation has been performed as this is a Phase I/II pilot study to evaluate safety. Up to five eyes in each disease group will be evaluated for safety and toxicity following IFN gamma-1b administered topically.

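### The replacement rule implies that participants who withdraw before five days of treatment fall outside the primary analysis, although the number of withdrawals is itself a primary outcome

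*Combined protocol and SAP*

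**What the plan says.** Section 3.0 (and the Précis, under Study Population) plans "Up to five participants with RCD with significant macular cystic changes and up to five participants with ESCS with significant macular cystic changes". It then adds that "up to an additional two participants may be enrolled in order to obtain the five participants in each disease group". The stated purpose of this allowance is to make up the number who are "included in the primary analysis if any participants withdraw from the study prior to receiving five days of treatment".

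Section 7.1 states that the primary outcome is "assessed by the number and severity of adverse events related to the IP and the number of withdrawals". The Précis gives the time point: "the number of withdrawals at 52 weeks (one year) post-administration". Neither place sets a minimum exposure.

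Section 8.1 says: "All reported adverse events will be tabulated and presented by system organ class, severity and relationship to study therapy". It does not say how withdrawals are counted or in which participants. Section 8.2 says: "Up to five eyes in each disease group will be evaluated for safety and toxicity following IFN gamma-1b administered topically". No section defines a safety analysis set.

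Three other provisions bear on the point. Section 6.1 lets an investigator withdraw a participant who has a serious adverse reaction. Section 4.4 lets the investigator reduce or stop the drops for ocular concerns while the participant stays in follow-up. Sections 13.2 and 13.3 set the safety review and stopping rules in terms of participants, with no five-day condition.

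**The concern.** Withdrawal plays two parts in this plan. It is counted as a primary outcome and, if it comes before five days of treatment, it is also the event that appears to take a participant out of the primary analysis. A set conditioned on staying in for at least five days can serve a description of efficacy. For tolerability, it selects on the outcome being measured.

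A drug-related withdrawal in that window is possible under the protocol's own terms, because section 6.1 allows withdrawal for a serious adverse reaction. Treatment lasts two weeks (section 4.4), so the window covers roughly the first third of the course (5/14 = 36%).

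Two things are at stake: the number of withdrawals reported, and the number of participants against which the adverse events are read. The study is descriptive and small, with no hypothesis tests (section 8.0), so these counts are the primary result. One or two people moved in or out change it visibly.

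**Working it through.** The plan states no proportion, interval, early-withdrawal rate or calculated sample size, so there is no figure of its own to reproduce. The check has two parts.

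**1. Does the text put early withdrawers outside the primary set?**

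- Section 3.0 and the Précis: extra people may be enrolled to obtain five per group for the primary analysis. If an early withdrawer still counted among the five, no extra person would be needed to reach five.
- Section 8.2: up to five eyes per group for safety. With replacements, a group could have six or seven treated eyes, and the section makes no allowance for them.
- Section 7.1 and the Précis: withdrawals are a primary outcome, with no five-day condition.
- Section 8.1: all reported adverse events are tabulated, with no five-day condition, no named population and no rule for withdrawals.

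The first two items imply exclusion. The last two do not. Nothing reconciles them.

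**2. How much could it matter?**

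Inputs: 5 + 5 = 10 planned participants (section 3.0). The extra two give 10 + 2 = 12 if they are a study total, or (5 + 2) × 2 = 14 if they are per group; the text does not say which. The number of early withdrawals is an assumption. Each early withdrawer is taken to have received at least one drop and to have been replaced, and nobody else withdraws.

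Intervals are exact (Clopper-Pearson) 95%. For x events in n, the lower limit is the 0.025 quantile of Beta(x, n − x + 1) and the upper limit is the 0.975 quantile of Beta(x + 1, n − x). For x = 0 the lower limit is 0 and the upper limit is 1 − 0.025^(1/n); with n = 10 this is 1 − 0.025^0.1 = 30.8%.

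| Assumed case | Early withdrawers left out | All treated counted |
|---|---|---|
| One early withdrawal | 0/10 = 0% (0 to 30.8%) | 1/11 = 9.1% (0.2 to 41.3%) |
| Two early withdrawals | 0/10 = 0% (0 to 30.8%) | 2/12 = 16.7% (2.1 to 48.4%) |
| Two, both in one disease group (that group only) | 0/5 = 0% (0 to 52.2%) | 2/7 = 28.6% (3.7 to 71.0%) |
| Four, if the allowance is two per group | 0/10 = 0% (0 to 30.8%) | 4/14 = 28.6% (8.4 to 58.1%) |

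The chance that the question arises at all, meaning at least one early withdrawal among the first ten, is 1 − (1 − p)^10 for an assumed true rate p:

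- p = 5%: 1 − 0.95^10 = 40%
- p = 10%: 1 − 0.90^10 = 65%
- p = 20%: 1 − 0.80^10 = 89%
- p = 30%: 1 − 0.70^10 = 97%

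**The case against.** A reader might infer that the plan removes early intolerance from the safety result altogether. The documents do not support that, for four reasons.

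- The replacement text is an enrolment rule. It is permissive and limited to two, and no sentence says that an early withdrawer's data are dropped.
- Section 8.1 tabulates all reported adverse events, and section 15.0 has them all summarized at continuing review. The events of a replaced participant should therefore appear.
- The trigger is withdrawal from the study. A participant who reacts, stops the drops under section 4.4 and stays in follow-up does not meet it, and that is the route the protocol provides for ocular concerns.
- The review and stopping provisions in sections 13.2 and 13.3 carry no five-day filter, so a replaced participant counts there.

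It can also be said that section 8.2 gives a planning number that merely omits the replacement allowance, and that the plan promises a number of withdrawals, with no proportion. On that view 0/10 is not something the plan commits itself to report.

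All of this stands as a limit on the point. It does not settle it. Section 8.1 is silent on withdrawals and on the population, and section 7.1 does not say whose withdrawals count. The stated purpose of the extra enrolment, to have five per group for the primary analysis, still points towards exclusion. An analyst could follow either reading after seeing the data.

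**Conclusion.** The point holds in a limited form. The Précis and sections 3.0 and 8.2 imply a primary set that leaves out people who withdraw before five days of treatment. Section 7.1 makes withdrawals a primary outcome without that condition. Followed as written, the rule can lower the primary withdrawal count and shrink the denominator for adverse events. The withdrawal component is the most exposed; the adverse event listing and the safety oversight are not affected.

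The effect is bounded by the number of participants replaced: at most two, or four if the allowance is per group, plus any further early withdrawers if they too are left out. The contrast of 0/10 with 2/12, or 0/5 with 2/7 in one group, illustrates an assumed case. It is neither a forecast nor a statement of what the plan will report. It rests on every early withdrawer being treated, replaced and uncounted. The documents give no early-withdrawal rate and no evidence that those who leave early would do so because of the drops.

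**What to change.** In the Précis and sections 3.0, 7.1 and 8.2:

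- Define the primary safety analysis set as every participant who received at least one drop of study product, whether or not later replaced. Replacements add to this set and do not substitute for anyone in it.
- Count and list every withdrawal, with its timing and reason.
- Confine any set that requires at least five days of treatment to the secondary efficacy descriptions in section 7.2.
- Align section 8.2 with the replacement allowance, and state whether the two extra participants are a study total (at most 12 treated) or per group (at most 14).

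Exact intervals around the proportions are optional in a descriptive pilot. The cost is wording in four places and no new data. The one downside is a possibly less favourable withdrawal count.

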3.1 Participant Eligibility Criteria

3.1.1 Inclusion Criteria

To be eligible, the following inclusion criteria must be met, where applicable.

1. Participant must be 12 years of age or older.
2. Participant (or legal guardian or legal representative) must understand and sign the protocol informed consent.
3. Participant is willing to comply with the study procedures and is expected to be able to return for all study visits.
4. Participant must carry a clinical diagnosis of RCD or ESCS.
5. ESCS participant must have molecular confirmation with two alleles for *NR2E3* gene mutations
6. Female participant of childbearing potential (see Appendix 5 for definition) must not be pregnant or breast-feeding, must have a negative pregnancy test at screening and must be willing to undergo pregnancy tests at scheduled study visits.
7. Female participant of childbearing potential (see Appendix 5), and any male participant able to father children must have (or have a partner who has) had a hysterectomy or vasectomy, be completely abstinent from intercourse or must agree to practice two reliable methods of contraception while taking the IP and six weeks after completion. Acceptable methods of contraception include:
 - Hormonal contraception (i.e., birth control pills, injected hormones, dermal patch or vaginal ring);
 - Intrauterine device;
 - Barrier methods (diaphragm, condom) with spermicide; or
 - Surgical sterilization (tubal ligation).

3.1.2 Exclusion Criteria

A participant is not eligible if any of the following exclusion criteria are present.

1. Participant has a history of other ocular disease likely to contribute significantly to visual disruption (e.g., optic neuropathy, glaucoma, uveitis, or other retinal disease).
2. Participant has had diagnosis or treatment of a malignancy (excluding non-melanoma skin cancer) within the previous five years.

3. Participant has received investigational treatment in another clinical study related to an ocular condition in the last six months.
4. Participant is pregnant, lactating, planning to become pregnant (or father a child) during the study follow-up period.
5. Participant is allergic to fluorescein dye.
6. Participant has a systemic condition that, in the opinion of the investigator, would preclude participation in the study (e.g., multiple sclerosis (MS), as IFN gamma may cause MS exacerbations).

3.2 Study Eye Eligibility Criteria

A participant must have at least one eye meeting all inclusion criteria and none of the exclusion criteria listed below.

3.2.1 Study Eye Inclusion Criteria

1. The study eye must retain adequate fixation to allow for completion of protocol assessments.
2. The study eye must have macular cystic changes (>275 microns and/or disruption of foveal contour on OCT).

3.2.2 Study Eye Exclusion Criteria

1. The study eye has lens, cornea, or other media opacities that preclude adequate visualization and testing of the retina.
2. The study eye has undergone intraocular surgery within 6 months prior to enrollment.
3. The study eye has a disease that may confound the outcome of the study [e.g., choroidal neovascularization (CNV) in the fovea or parafoveal area].
4. Participant is unwilling to discontinue wearing a contact lens in the study eye during IP administration.

